### **3.1 Study Endpoints:**

#### ***Primary Endpoint(s):***

- Percentage of Patients achieving Eczema Area and Severity Index-75 (EASI-75) ( $\geq 75\%$  improvement from baseline) at week 16.

#### ***Secondary Endpoints:***

- Percentage of patients achieving  $\geq 4$ -point improvement (reduction) in the weekly average peak daily Pruritus Numeric Rating Scale (NRS) score from baseline to weeks 4, 8, 12, 16, and 32 in patients with baseline score  $\geq 4$ .\*
- Percentage of patients achieving  $\geq 4$ -point improvement (reduction) in the weekly average overall Pruritus Numeric Rating (NRS) from baseline to weeks 4, 8, 12 16, and 32 in patients with baseline score  $\geq 4$ .\*

- Percentage of patients achieving  $\geq 4$ -point improvement (reduction) in the weekly average peak daily Pain Numeric Rating Scale (NRS) score from baseline to weeks 4, 8, 12, 16, and 32 in patients with baseline score  $\geq 4$ .\*
- Percentage of patients achieving  $\geq 4$ -point improvement (reduction) in the weekly average overall Pain Numeric Rating (NRS) from baseline to weeks 4, 8, 12, 16, and 32 in patients with baseline score  $\geq 4$ .\*
- Percentage of patients achieving EASI-75 ( $\geq 75\%$  improvement in Eczema Area and Severity Index Score [EASI] from baseline) at weeks 4, 8, 12, and 32.\*
- Percentage of patients achieving an Investigators Global Assessment (IGA) score of 0 or 1 (on a 5-point scale) and a reduction in this measure from baseline of at least 2 points at week 16.
- Percentage of patients achieving EASI-90 ( $\geq 90\%$  improvement in Eczema Area and Severity Index Score [EASI] from baseline) at weeks 12, 16, and 32.\*
- Change in Dermatology Life Quality Index (DLQI) from baseline to weeks 8, 12, 16, and 32.\*
- Change in Hospital Anxiety Depression Scale (HADS) (Anxiety) from baseline to weeks 8, 12, 16, and 32.\*
- Change in Hospital Anxiety Depression Scale (HADS) (Depression) from baseline to weeks 8, 12, 16, and 32.\*
- Change in Patient Oriented Eczema Measure (POEM) Scores from baseline to weeks 8, 12, 16, and 32.\*
- Change in SCORing Atopic Dermatitis (SCORAD) score from baseline to weeks 8, 12, 16, and 32.\*
- Change in Global Individual Signs Score (GISS) from baseline to weeks 8, 12, 16, and 32.\*

***Exploratory Endpoints:***

- Percentage of patients achieving an IGA score 0 or 1 (on a 5-point scale) and a reduction in this measure from baseline of at least 2 points at week 12.
- Change in Eczema Area and Severity Index Score (EASI) from baseline to weeks 8, 12, 16, and 32.
- Change from baseline to week 4 in Dermatology Life Quality Index (DLQI).
- Patients (%) achieving 50% reduction in SCORAD Score at Weeks 4, 8, 12, 16, and 32.\*
- Patients (%) achieving 75% reduction in SCORAD Score at Weeks 4, 8, 12, 16, and 32.\*
- Patients (%) achieving 90% reduction in SCORAD Score at Weeks 4, 8, 12, 16, and 32.\*
- Change from baseline to week 8, 12, 16, and 32 in percent Body Surface Area (BSA).\*

***Safety Endpoints:***

- Incidence of skin infection treatment-emergent adverse events (TEAEs) requiring systemic treatment from baseline through week 16 and 32.
- Incidence of treatment-emergent serious adverse events (TESAEs) from baseline through week 16 and 32.
- Incidence of TEAEs leading to treatment discontinuation from baseline through week 16 and 32.

\*Each listed time point (in weeks) will be measured separately and treated as an individual endpoint.

## 4. ELIGIBILITY CRITERIA

### 4.1 INCLUSION CRITERIA

**No waivers/exemptions will be granted for protocol inclusion/exclusion criteria.**

Subjects are included in the study if they meet all of the following criteria:

- Written informed consent provided by the patient.
- Male or female, at least 18 years.
- Willing and able to attend all clinic visits and comply with study-related procedures
- Is able to understand and complete study-related questionnaires
- Chronic atopic dermatitis present for at least 3 years.
- EASI score  $\geq 16$  at screening and baseline visits.
- IGA score  $\geq 3$  at screening and baseline visits.
- Baseline pruritis numerical rating scale average score for maximum intensity of at least 3, based on the average of daily pruritis numerical rating scale scores for maximum itch intensity reported during the 7 days prior to randomization.
- Has applied a stable dose of topical moisturizer twice daily for at least 7 consecutive days immediately prior to the baseline visit and is willing to continue this regimen on a daily basis for the duration of the study.
- $\geq 10\%$  body surface area (BSA) of AD involvement at screening and baseline visits.
- Documented recent history (within 6 months prior to screening) of inadequate response to treatment with topical medications, or patients for whom topical treatments are medically inadvisable (because of important side effects or safety risks).
  - a) Inadequate response is defined as failure to achieve and maintain remission or a low disease activity state (comparable to an IGA score of 0-2), despite treatment with a daily regimen of topical corticosteroids of medium to higher potency (with or without topical calcineurin inhibitors as appropriate), applied for at least 28 days or for the maximum duration recommended by the product prescribing information, whichever is shorter.
  - b) Patients with documented systemic treatment for atopic dermatitis in the preceding 6 months are also considered to be inadequate responders to topical treatments and are potentially eligible for treatment with bermekimab, after appropriate washout.
  - c) Important side effects or risks are those that outweigh the potential treatment benefits, and include: intolerance to treatment, hypersensitivity reactions, significant skin atrophy, and adverse systemic effects.

- d) Acceptable documentation includes contemporaneous chart notes that record topical medication prescription and treatment outcome, or investigator documentation based on communication with the patient's treating physician.

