##### **2.4.1.2. Per Protocol Analysis Set**

The primary endpoint will also be analyzed using the per-protocol population, which includes participants who are generally compliant with the protocol.

Specifically, the per protocol population includes participants in FAS except those

- who did not meet the inclusion criteria in the protocol as listed below:
  - EASI score  $\geq 16$  at screening and baseline visits.
  - IGA score  $\geq 3$  at screening and baseline visits.
  - $\geq 10\%$  body surface area (BSA) of AD involvement at screening and baseline visits.

- NRS Weekly Average of worst daily Skin Itch Scores at least 3 at screening
- who did not receive all scheduled study agent administrations prior to Week 16.

However, for those who discontinued the study agent prior to Week 16 will be included in the per protocol analysis and the data handling rule specified in section 5.2.2 will apply.

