### **5.2.2. Data Handling Rules**

No imputation will be performed for missing baseline values.

For the main analysis of primary endpoint of EASI-75 response at Week 16, a subject who discontinued treatment will be considered as a non-responder from that point onward. The remaining missing data will be imputed as non-responder. Supplementary analyses will be performed and include (1) using observed data regardless of whether the subject discontinued treatment or have missing data, and (2) data after treatment discontinuation will be considered as missing, missing response will be imputed by multiple imputation methods under the assumption of missing at random. Similar data handling rules (i.e., main analysis with non-responder imputation and 2 supplementary analyses) will also be applied for EASI-75 response over time through Week 16. The following data handling rules will be applied for other endpoints:

Binary secondary endpoints:

- Analyses will be similar to the main analysis of the primary endpoint. A subject who discontinued treatment will be considered as a non-responder from that point onward. The remaining missing data will be imputed as non-responder. Supplementary analyses will be performed for selected endpoint (i.e IGA responses) in the same manner as the primary endpoint.

Continuous secondary endpoints:

- If a subject discontinued treatment, zero will be assigned to improvement or percent improvement. Remaining missing data will not be imputed. A MMRM model will adjust for missing post baseline data and all available data from the 3 treatment groups through Week 16 or from Week 16 through Week 36 will be included. Under the assumption of missing at random (MAR), the missing data will be accounted for through correlation of repeated measures in the model. Supplementary analyses will be performed for selected endpoints (i.e. EASI total score, NRS itch score) and include (1) using observed data regardless of whether the subject discontinued treatment or have missing data, and (2) data after treatment discontinuation will be considered as missing, missing data will be addressed by MMRM model.

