### **5.4.3. Numerical Rating Scale (NRS) for Itch & Pain**

#### **5.4.3.1. Definition**

Patients will be given a diary to complete each night before bed. Patients will be asked to report “average pain”, and “worst moment pain” as well as “average itch” and “worst moment itch” on a 0-10 numeric rating scale. Patient diaries will be collected weekly. A higher score indicates more severe disease (0 indicate no itch or no pain). The baseline is defined as the average score of last 7 days prior to Week 0 study agent administration. If there are more than 3 days missing data, then baseline is set as missing. Missing baseline will not be imputed.

Seven daily NRS scores are averaged into a weekly score (ie 7 days [from day -7 to -1] prior to a visit). Four days out of 7 days (either consecutive or nonconsecutive) are necessary to derive a weekly score; otherwise data are considered missing for that week.

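### The itch entry criterion sets no minimum number of diary days, so a patient can be validly enrolled on 1 to 3 entries that the SAP will not accept as an NRS baseline

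*Protocol*

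**What the plan says.** **Entry.** Protocol 4.1, repeated in the synopsis, asks for a "Baseline pruritis numerical rating scale average score for maximum intensity of at least 3". It then defines how that value is formed: "based on the average of daily pruritis numerical rating scale scores for maximum itch intensity reported during the 7 days prior to randomization". No inclusion or exclusion criterion says how many of the seven days must be filled in. The nearest safeguard concerns ability: "Is able to understand and complete study-related questionnaires".

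**Analysis baseline.** SAP 5.4.3.1 uses a different anchor and adds a completeness rule: "The baseline is defined as the average score of last 7 days prior to Week 0 study agent administration". It continues: "If there are more than 3 days missing data, then baseline is set as missing. Missing baseline will not be imputed". SAP 5.2.2 gives the same rule for all endpoints: "No imputation will be performed for missing baseline values".

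**Per-protocol set.** SAP 2.4.1.2 lists the itch rule among the protocol inclusion criteria, but words it as "NRS Weekly Average of worst daily Skin Itch Scores at least 3 at screening". The EASI, IGA and BSA items in the same list refer to both the screening and the baseline visits.

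**The concern.** The score that decides entry and the score that serves as the analysis baseline should be the same quantity. They differ in two respects: the number of days needed, and the date from which the seven days are counted. A site that follows 4.1 to the letter can enrol someone whose baseline the SAP then sets to missing.

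After the first dose that baseline cannot be recovered. Every analysis in SAP 5.4.3.2 is either an improvement from baseline or a 4-point response among patients whose baseline is at least 4, so each one needs it. At stake is information on itch and pain, the patient-reported symptoms that head the protocol's list of secondary endpoints.

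**Working it through.** **1. The plan's own figure.** The only design calculation is for EASI-75 (protocol 10.1): 60% versus 20%, two-sided 0.05, 80% power. With pooled variance, n = [1.960·√(2·0.4·0.6) + 0.842·√(0.6·0.4 + 0.2·0.8)]² / 0.4² = (1.358 + 0.532)² / 0.16 = 22.3, so 23 per arm. This agrees with the plan. The point here does not depend on it; the documents give no figure for diary completion.

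**2. The two rules by day count.**

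| Diary days available | Days missing | Mean for entry can be formed (4.1) | SAP baseline |
|---|---|---|---|
| 0 | 7 | no | missing |
| 1, 2 or 3 | 6, 5 or 4 | yes | missing |
| 4 to 7 | 3 to 0 | yes | valid |

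The gap is the middle row: entries on 1 to 3 days averaging at least 3.

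**3. Whether a later rule restores the patient.**
- Responder endpoints: non-responder imputation (SAP 5.2.2) fills in a missing response. It cannot place a patient in a denominator defined by a baseline of at least 4 when the baseline is unknown.
- Continuous endpoints: the MMRM (SAP 5.1) has the baseline value as a model term, and the improvement itself is undefined without it.

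**4. Which endpoints.** One nightly diary holds average and worst itch and average and worst pain (protocol 8.2). If only the worst-itch item is skipped, the other three baselines can survive. If whole nights are missed, all four go. The protocol lists 4 scores × 5 weeks (4, 8, 12, 16, 32) = 20 NRS responder endpoints. SAP 5.4.3.2 plans treatment comparisons for them only at Week 16 and summarizes the other weeks.

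**5. The window.** The protocol 5.2.1 calendar places randomization in the screening column, while the SAP counts back from the Week 0 dose. When the two dates differ, even a patient with a full diary before randomization may lack 4 of 7 days before dosing.

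**6. Size, on an assumed completion rate.** Let each day be completed independently with probability p, and treat the two windows as one. Then P(1 to 3 days) = Σₖ₌₁³ C(7,k)·pᵏ·(1−p)⁷⁻ᵏ.
- p = 0.9: 0.0000063 + 0.0001701 + 0.0025515 = 0.0027; × 90 = 0.25 patients.
- p = 0.8: 0.00036 + 0.00430 + 0.02867 = 0.0333; × 90 = 3.0 patients, or 1 per arm of 30.
- Sensitivity only: p = 0.7 gives 0.126 (11.3 patients) and p = 0.6 gives 0.288 (25.9 patients).

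Losing 1 of 30 per arm inflates a standard error by √(30/29) = 1.017, about 1.7%. For the responder endpoints the counts are upper figures under each assumption, because some of these patients would have a baseline between 3 and 4 and fall outside the denominator anyway.

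**The case against.** **An eligibility rule and an analysis rule need not match.** Protocol section 10 leaves detail to the SAP, and both rules are seven-day averages taken shortly before treatment. That is fair, and it would be too strong to call the definitions incompatible. The practical gap remains, because an analysis rule does not bind a site at enrolment.

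**Soft safeguards exist.** Patients must be able to complete questionnaires and willing to follow procedures, investigators may exclude patients likely to be unreliable (4.2), and Visit 1 requires all criteria to be verified again. These make enrolment on 1 to 3 entries less likely. None of them sets a day count.

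**Stronger readings a reader might infer, which the documents do not support:**
- *That these patients leave the full analysis set.* Membership needs only randomization and one dose (SAP 2.4.1.1).
- *That 20 treatment comparisons are damaged.* Comparisons are planned at Week 16 only, and loss across all four scores requires whole missed nights.
- *That the randomized comparison is biased.* The missing entries precede treatment, so by themselves they cost precision.
- *That 11 or 26 patients will be lost.* Those figures come from assumed completion of 70% or 60%, applied to all 90 patients as if the safeguards did nothing.
- *That the per-protocol itch rule cannot be applied because the diary is only issued at screening.* Screening is a period of up to 30 days with a daily diary, so a weekly average can be formed within it. The rule does not say which week, so it is misaligned with 4.1 rather than unusable.

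**A hard rule has a price.** No waivers are allowed, so a patient who never reaches four entries would be a screen failure and would also be lost to the EASI-75 analysis. This stands as a cost of the change.

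**Conclusion.** The mismatch holds. As written, a patient with 1 to 3 worst-itch entries averaging at least 3 satisfies the itch criterion and has no worst-itch baseline. No rule in the SAP brings that patient back into the worst-itch analyses, nor into the average-itch and pain analyses when whole nights were missed.

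The consequence is modest: about 0 to 3 of 90 patients at 90% to 80% daily completion, more if completion is lower. This rests on independent days and on completion rates that the documents do not give. The endpoints concerned are secondary with nominal p-values. The point is a cheap improvement to make before an irrecoverable loss, not a threat to the trial's main conclusion.

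**What to change.** 1. In the synopsis and protocol 4.1, require the average worst-itch score of at least 3 to come from at least 4 of 7 daily entries, in the same seven-day window that SAP 5.4.3.1 uses for baseline.
2. Have sites check the count before randomization and again at Visit 1, where the criteria are already re-verified. If the count is not met, postpone randomization within the 30-day screening window. Keep randomization close to Visit 1 so that the two checks cover nearly the same days; a patient who passes the first and fails the second would be randomized but untreated.
3. In SAP 2.4.1.2, replace the reference to screening in the itch item with this same definition.

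The change amounts to one sentence in each document, plus the same edit in the synopsis, and borrows a threshold the SAP already uses. The downside is a short delay for some patients and an occasional screen failure, softened by the single re-screening that the protocol allows. A count on worst itch does not guarantee the average-itch and pain baselines, but with one nightly diary it will usually secure them.

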## 4.2 EXCLUSION CRITERIA

Subjects with ANY of the following will be excluded from the study:

- Age below 18 years as the current study is evaluating bermekimab in adult patients only
- Subject has been treated for AD with any investigational drug of chemical or biologic nature within a minimum of 30 days or 5 half-lives (whichever is longer) of the drug prior to baseline
- Treatment with bermekimab at any time in the past.
- Treatment with immunosuppressive/immunomodulatory drugs or phototherapy for atopic dermatitis within 4 weeks of baseline, or any condition that, in the opinion of the investigator, is likely to require such treatment(s) during the first 4 weeks of study treatment
- Treatment with topical corticosteroids or topical calcineurin inhibitors for the treatment of AD within 14 days prior to baseline]
- Treatment with biologics as follows:
  - a) Any cell-depleting agents including, but not limited to, rituximab, within 5 half-lives (if known) or 30 days prior to baseline visit, or until lymphocyte count returns to normal, whichever is longer.
  - b) Other biologics: within 5 half-lives (if known) or 30 days prior to baseline visit, whichever is longer
- Initiation of treatment of atopic dermatitis with prescription moisturizers or moisturizers containing additives such as ceramide, hyaluronic acid, urea, or filaggrin degradation products during the screening period (patients may continue to use stable doses of such moisturizers if initiated before the screening visit)
- Regular use (more than 2 visits per week) of a tanning booth/parlor within 4 weeks of the screening visit
- Planned or anticipated use of any prohibited medications and procedures during study treatment
- Treatment with a live (attenuated) vaccine within 30 days prior to the screening visit
- Active chronic or acute infection requiring treatment with systemic antibiotics, antivirals, antiparasitics, antiprotozoals, or antifungals within 2 weeks prior to the baseline visit, or superficial skin infections within 1 week prior to the baseline visit. NOTE: patients may be rescreened after infection resolves

- Known or suspected history of immunosuppression, including history of invasive opportunistic infections (e.g., tuberculosis, histoplasmosis, listeriosis, coccidioidomycosis, pneumocystis, aspergillosis) despite infection resolution; or unusually frequent, recurrent, or prolonged infections, per investigator judgment.
- History of human immunodeficiency virus (HIV) infection or positive HIV serology at screening
- Positive for hepatitis B surface antigen, hepatitis B core antibody, or hepatitis C antibody at the screening visit
- At baseline, presence of any conditions listed as criteria for study drug discontinuation
- Presence of skin comorbidities that may interfere with study assessments
- History of malignancy within 5 years before the screening visit, except completely treated in situ carcinoma of the cervix, and completely treated and resolved non-metastatic squamous or basal cell carcinoma of the skin.
- Severe concomitant illness(es) that, in the investigator's judgment, would adversely affect the patient's participation in the study. Examples include, but are not limited to, patients with short life expectancy, patients with uncontrolled diabetes ( $HbA1c \geq 9\%$ ), patients with cardiovascular conditions (eg, stage III or IV cardiac failure according to the New York Heart Association classification), severe renal conditions (eg, patients on dialysis), hepato-biliary conditions (eg, Child-Pugh class B or C), neurological conditions (eg, demyelinating diseases), active major autoimmune diseases (eg, lupus, inflammatory bowel disease, rheumatoid arthritis, etc.), other severe endocrinological, gastrointestinal, metabolic, pulmonary or lymphatic diseases. The specific justification for patients excluded under this criterion will be noted in study documents (chart notes, case report forms [CRFs], etc.)
- Planned or anticipated major surgical procedure during the patient's participation in this study
- Patient or immediate family member is part of the current clinical investigational team
- Pregnant or breastfeeding women, or women planning to become pregnant or breastfeed during the study
- Women unwilling to use adequate birth control, if of reproductive potential and sexually active. Adequate birth control is defined as consistent practice of an effective and accepted method of contraception throughout the duration of the study and for 120 days after the last dose of study drug. These methods include oral contraceptives (stable use for more than 3 months before Screening), intrauterine device (IUD), hormonal contraceptives such as Depo-Provera (stable use for more than 3 months before Screening), Implanon implants (stable use for more than 3 months before Screening), double barrier contraception such as condom or diaphragm used with

contraceptive sponge, foam, or jelly. For men participating in the study, unwillingness of sexual partner to use any of the above contraception methods.

- History of severe allergic or anaphylactic reactions to monoclonal antibodies.
- Any other medical or psychological condition (including relevant laboratory abnormalities at screening) that, in the opinion the investigator, may suggest a new and/or insufficiently understood disease, may present an unreasonable risk to the study patient as a result of his/her participation in the study, may make patient's participation unreliable, or may interfere with study assessments. The specific justification for patients excluded under this criterion will be noted in study documents (chart notes, case report forms, etc.)

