### **2.9.3 Permitted Medications and Procedures**

Use of concomitant medications is permitted if not listed in section 2.9 Prohibited Medications and Procedures. Permitted concomitant medications includes basic skin care (cleansing and bathing, including bleach baths), moisturizers (required as background treatment), topical anesthetics, antihistamines, and topical and systemic anti-infective medications for any duration. In addition, medications used to treat chronic disease such as diabetes, hypertension, and asthma are permitted.

Any questions regarding treatment with concomitant medication during the study, should be directed to the medical monitor.

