## **2.10 PROHIBITED MEDICATIONS AND PROCEDURES**

Treatment with the following concomitant medications is *prohibited* during the entire duration of the study:

- Topical tacrolimus and pimecrolimus
- Treatment with a live (attenuated) vaccine
- Treatment with other investigational drugs (besides Bermekimab)
- Treatment with topical corticosteroids or topical calcineurin inhibitors; such agents may be administered during the study only if required for atopic dermatitis rescue. If topical corticosteroids and/or topical calcineurin inhibitors are used during the study, study treatment may continue as planned.
- Treatment with systemic corticosteroids or nonsteroidal systemic immunosuppressive drugs (e.g., cyclosporine, methotrexate, mycophenolate-mofetil, azathioprine, etc.), except if required for atopic dermatitis rescue, or if critically medically needed to treat concurrent medical conditions (e.g., asthma).
  - The use of systemic corticosteroids for indications other than AD should be limited to situations for which, in the opinion of the treating physician, there are no adequate alternatives. They should be used on a short-term basis, preferably for  $\leq 2$  weeks. Longer-term use of corticosteroids should be discussed with the medical monitor or designee and may require discontinuation of study drug. Inhaled, otic, ocular, nasal or other routes of mucosal delivery of corticosteroids are allowed throughout the study.
- Leukotriene inhibitors

- Allergen immunotherapy
- Systemic treatment for AD with an immunosuppressive/immunomodulating substance (including, but not limited to, cyclosporine, mycophenolate-mofetil, IFN- $\gamma$ , azathioprine, methotrexate, or biologics)

Study drug will be discontinued if any of the following are used through week 16:

- Treatment with a live (attenuated) vaccine
- Treatment with investigational drugs other than bermekimab.
- Treatment with systemic corticosteroids or nonsteroidal systemic immunosuppressive drugs (e.g., cyclosporine, methotrexate, mycophenolate-mofetil, azathioprine, etc.)

The following concomitant procedures are prohibited during study participation:

- Surgical procedures
- Concomitant ultraviolet (UV) procedures (phototherapy [NBUVB, UVB, UVA1, or PUVA])
- Tanning in a bed/booth
- Patients are not allowed more than 2 bleach baths per week during study participation

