## **3. STUDY DESIGN AND OBJECTIVES**

This is a phase II, randomized, double-blind, placebo-controlled study to further establish the efficacy and safety and explore dose effects for bermekimab monotherapy in adults with moderate to severe Atopic Dermatitis (AD). Patients will be assessed for study eligibility at the initial screening visit after providing informed consent. Thirty days are allowed in the screening window to complete all screening procedures and randomize the subject. During the screening period, certain treatments will be washed out, as

applicable, according to eligibility requirements. Patients who fail initially may be re-screened once based on the investigator discretion but only if inclusion criteria are met at time of re-screening.

The study is approximately 40 weeks (30 day screening period, 32-week treatment period and a 4-week follow-up period) for all subjects.

Patients who meet the eligibility criteria at screening will be randomized in a 1:1:1 ratio to one of two treatment arms or placebo:

- Arm 1: 800 mg of bermekimab + placebo loading dose (2mL SC injection containing 400 mg of bermekimab and one 2mL SC injection of placebo) at week 0 followed by weekly (qw) subcutaneous (SC) injections of 400 mg bermekimab through week 31
- Arm 2: 800 mg loading dose of bermekimab (2 x 400 mg SC injections) at week 0 followed by subcutaneous (SC) injections of 400 mg bermekimab every other week (q2w) alternating with matching placebo q2w through week 31
- Arm 3: 4mL loading dose of placebo (2 x 2mL SC injections) at week 0 followed by weekly placebo injections from weeks 2 through week 15. Patients in Arm 3 will begin to receive weekly (qw) blinded subcutaneous (SC) injections of 400 mg bermekimab beginning at week 16 through week 31.

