## 4.6. Concomitant Medications

Concomitant medications for atopic dermatitis will be summarized by treatment group for the FAS. Prior medications are defined as any therapy used before the day of first dose (partial or complete) of study agent. Concomitant medications are defined as any therapy used on or after the same day as the first dose of study agent, including those that started before and continued after the first dose of study agent.

A list of participants who received a concomitant treatment that could improve AD will be provided.

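### In a monotherapy trial, the treatment-period medication list leaves other active topical AD drugs permitted, and no analysis rule stops their users counting as EASI-75 responders at Week 16

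*Protocol*

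**What the plan says.** **Aim.** Protocol section 3 sets out to "explore dose effects for bermekimab monotherapy in adults with moderate to severe Atopic Dermatitis (AD").

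**Before baseline.** Protocol 4.2 (repeated in the synopsis) has two relevant bullets:
- The topical washout: "Treatment with topical corticosteroids or topical calcineurin inhibitors for the treatment of AD within 14 days prior to baseline".
- A separate exclusion: "Treatment with immunosuppressive/immunomodulatory drugs or phototherapy for atopic dermatitis within 4 weeks of baseline". It names no route of administration. It also excludes patients whose condition is judged likely to need such treatment in the first 4 weeks on study.

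**During treatment.** Protocol 2.10 lists:
- "Topical tacrolimus and pimecrolimus"
- "Treatment with topical corticosteroids or topical calcineurin inhibitors; such agents may be administered during the study only if required for atopic dermatitis rescue"
- "Systemic treatment for AD with an immunosuppressive/immunomodulating substance"

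A further bullet covers systemic corticosteroids and nonsteroidal systemic immunosuppressants. The default for everything else is in 2.9.3: "Use of concomitant medications is permitted if not listed in section 2.9 Prohibited Medications and Procedures". The list is in fact in 2.10.

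**Analysis.**
- Protocol 10.5.3.1 makes a patient a non-responder once rescue begins.
- The SAP 5.3.2 composite estimand treats protocol-specified rescue as part of the regimen and names one intercurrent event, treatment discontinuation. SAP 5.3.3 adds only missing Week 16 data.
- SAP 4.6 says: "A list of participants who received a concomitant treatment that could improve AD will be provided".

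**The concern.** A site reading 2.9.3 and 2.10 together finds no bar to a non-investigational topical AD drug outside the two named classes. Such use would not be an excluded therapy, so the deviation category for excluded concomitant treatment in SAP 4.5 would not catch it. The per-protocol set in SAP 2.4.1.2 removes patients for four entry criteria and for missed doses, not for concomitant treatment.

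A patient who reaches EASI-75 with help from such a drug would then count as a success in the primary analysis. If use is concentrated among patients doing badly, it lifts placebo more than active and shrinks the difference. If it happened to be heavier on active, it would inflate the difference. In either case the result is no longer a clean monotherapy comparison, and the primary analysis makes no adjustment.

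**Working it through.** **1. Is the use permitted, and does any rule catch it?**

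| Stage | Two named topical classes | Another marketed topical AD drug |
|---|---|---|
| Before baseline (4.2) | 14-day exclusion | Unclear: depends on whether the 4-week exclusion covers topicals |
| On study (2.10, 2.9.3) | Only as rescue | Not listed, so permitted |
| Deviation (SAP 4.5) | Yes, if not rescue | No |
| Per-protocol set (SAP 2.4.1.2) | Not removed | Not removed |
| EASI-75, protocol 10.5.3.1 | Non-responder if rescue | Non-responder only if recorded as rescue |
| EASI-75, SAP 5.3.2 and 5.3.3 | No rule | No rule |
| SAP 4.6 | Listed | Listed |

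On the entry row: if the 4-week exclusion reaches topicals, it overlaps the 14-day window for topical calcineurin inhibitors in the same list. If it does not, other topicals have no washout. The text does not settle which is meant.

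**2. The plan's own figure.** Inputs (Protocol 10.1, SAP 1.4): 60% v 20%, two-sided 0.05, Pearson chi-square, 23 per arm for about 80% power, about 90 randomized 1:1:1 (30 per arm).

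n per arm = [1.96·√(2p̄q̄) + 0.842·√(p₁q₁+p₂q₂)]² / (p₁−p₂)², with p̄ = 0.40
= [1.96·√0.48 + 0.842·√0.40]² / 0.40² ≈ 22.3, so 23. This reproduces.

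The matching power is 81.2% at 23 per arm and 90.6% at 30 per arm.

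**3. Possible size.** The documents give neither a usage rate nor an effect of such drugs. Assumptions: a share s = 10–30% of would-be non-responders use one, and c = 25–40% of users reach EASI-75 because of it. Would-be non-responders are 80% on placebo and 40% on active.

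- Rise on placebo = 0.80·s·c: from 0.80×0.10×0.25 = 0.020 to 0.80×0.30×0.40 = 0.096.
- Rise on active = 0.40·s·c: from 0.40×0.10×0.25 = 0.010 to 0.40×0.30×0.40 = 0.048.

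| Scenario | Rates, low to high assumption | Difference (points) | Power, 30 per arm |
|---|---|---|---|
| As planned | 60 v 20 | 40 | 90.6% |
| Equal use in both arms | 61.0 v 22.0 to 64.8 v 29.6 | 39.0 to 35.2 (loss 1.0–4.8) | 88.6% to 79.5% |
| Placebo only | 60 v 22.0 to 60 v 29.6 | 38.0 to 30.4 (loss 2.0–9.6) | 86.8% to 66.6% |
| Active only | 61.0 v 20 to 64.8 v 20 | 41.0 to 44.8 (gain 1.0–4.8) | Apparent effect inflated |

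**The case against.** The strongest reply has four parts.

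- **Entry.** The 4-week exclusion has no route limit, whereas 2.10 says systemic where that is meant. The 14-day rule could be a specific exception within a general one. A reader might infer that other topicals need no washout at all; the text is unclear, and that is as far as it goes. A reader might also think the exclusion has no bearing after Day 0, but it screens on expected need during the first 4 weeks of treatment. This part stands.
- **Rescue.** Patients doing badly would mostly be treated as rescue. Section 2.11 speaks of topical medications in general as first line, and 10.5.3.1 then makes them non-responders. This stands for use recorded as rescue, under the protocol. It does not reach a permitted topical that nobody labels rescue, and the SAP estimand omits the rule.
- **Size.** Usage is assumed, and the placebo-only range needs no use at all among active-arm non-responders, which is hard to defend under double-blinding. This stands. With equal use, power at 30 per arm stays close to 80% even at the top of the assumed range.
- **Other safeguards.** Starting prescription or additive-containing moisturizers is barred (2.9.2), investigational drugs are barred (2.10), and the medical monitor takes questions (2.9.3). These narrow the gap without closing it: a marketed topical drug is neither a moisturizer nor investigational, and a site told that unlisted drugs are permitted has no reason to ask.

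**Conclusion.** The treatment-period gap holds on a plain reading. A non-investigational topical AD drug outside the two named classes may be used through Week 16, is not a deviation, and can contribute to an EASI-75 response unless recorded as rescue. Under the SAP as written, recording it as rescue would not change the result either. At entry the finding is ambiguity only.

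The size is unknown. Under the stated assumptions the loss is 1.0–4.8 points with equal use, and 2.0–9.6 points is an extreme, not an expectation. Small usage means a small effect, and the direction is not guaranteed.

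A reader might also infer that widening the list in 2.10 would be enough. It would not: drugs brought under the existing topical rule could still be given as rescue with study treatment continuing, and the SAP would still count an EASI-75 reached on them. The analysis rule has to change too.

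**What to change.** **Protocol.** Reconcile 2.9.3, 2.10 and 4.2 (and the synopsis) with the monotherapy aim:
- state whether the 4-week exclusion covers topical drugs, and how it relates to the 14-day window;
- state in 2.10 the status of topical AD drugs outside the two named classes;
- correct the cross-reference in 2.9.3 from 2.9 to 2.10.

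Which drugs are allowed, and with what washout, is for the sponsor to set.

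**SAP 5.2.2, 5.3.2 and 5.3.3.** Carry over the rule in Protocol 10.5.3.1, so that rescue users are non-responders once rescue starts. Apply the same handling to any concomitant treatment that could improve AD (already to be identified for the SAP 4.6 listing) started before Week 16, at least as a stated sensitivity analysis. Define that category before the Week 16 database lock, when some sponsor staff are unblinded. Make clear that the required moisturizers do not trigger it, and say how a drug continued from before baseline is treated, since SAP 4.6 counts it as concomitant.

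**Cost.** A few lines of protocol text, a little more analysis work and possibly slightly lower response rates. In the model above, where only would-be non-responders use such drugs, the rule returns the rates to 60% v 20%. If would-be responders use them too, rates fall below that.
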